### **Pregnancy**

Before study enrollment, subjects must agree to take appropriate measures to avoid pregnancy. However, should a pregnancy occur (including female partners of male subjects), the subject will consent to provide follow-up information regarding the outcome of the pregnancy and the health of the infant until 30 days old.

A patient must immediately inform the investigator if the patient or patient's partner becomes pregnant from the time of consent to 30 days after the last dose of study drug. Any female patients receiving PCI-32765 who become pregnant must immediately discontinue study drug. The investigator should counsel the patient, discussing any risks of continuing the pregnancy and any possible effects on the fetus.

Although pregnancy itself is not regarded as an AE, the outcome will need to be documented. Report any pregnancy that occurs in a subject or subject's partner from the time of consent to 30 days after the last dose of study drug. Record any occurrence of pregnancy on appropriate case report form and fax it to Pharmacocyclics Drug Safety, or designee, within 24 hours of learning of the event. The pregnant female will be followed for outcome, which is defined as elective termination of the pregnancy, miscarriage, or delivery of the fetus. For pregnancies with an outcome of live birth, the newborn infant will be followed until 30 days old by completing the Pregnancy Report Form Part II. Any congenital anomaly/birth defect noted in the infant must be reported as an SAE. .

**Expedited Reporting Requirements for SAEs and Fatal or Life-Threatening Suspected Adverse Reaction Reports**

Investigators of studies conducted under an IND must comply with the following safety reporting requirements.

The investigator must submit each IND safety report in a narrative format or on FDA Form 3500A or in an electronic format that FDA can process, review and archive. A copy of this IND safety report must also be faxed to Pharmacyclics Drug Safety.

The investigator must notify FDA and Pharmacyclics of any serious, unexpected, suspected adverse reaction observed during the conduct of the study as soon as possible but in no case later than 15 calendar days after becoming aware of the occurrence.

The investigator must notify FDA and Pharmacyclics of any unexpected fatal or life-threatening suspected adverse reaction as soon as possible, but no later than 7 calendar days after the Sponsor's receipt of the information.

Upon request from the FDA or Pharmacyclics additional data or information that the agency or Pharmacyclics deems necessary, must be reported as soon as possible but no later than 15 calendar days.

FDA Contact	
Pharmacyclics Drug Safety Contact Information	
US Local [contact]
US Toll Free [contact]

### 13.0 Statistical Considerations

The primary objectives of the statistical analysis will be (1) to demonstrate that there is a population of CLL cells that do not leave or take sanctuary outside of the peripheral blood system in solid lymphoid tissues, (2) to describe the longitudinal pattern in observed labeled cells and (3) to estimate rates of cell death.

For purposes of statistical analysis, the experiment will be divided into two periods (with each period, itself, being divided into two subperiods): Period 1 corresponds to the non-interventional period when heavy water is consumed for 4 weeks (Period 1a) and then discontinued (Period 1b) so that a CLL cell disappearance rate can be tracked over time.

Period 2 corresponds to the interventional period when Btk inhibitor (PCI-32765) is administered to subjects. Assuming that the observed percentage of labeled cells (LC) reaches a peak at some point in time,  $T$ , then Period 2a is defined as the “pre-peak” sub-period (i.e., all times  $t \leq T$ ) and Period 2b is the “post-peak” sub-period ( $t > T$ ).

[figure not shown]
[figure not shown]
Strictly speaking, Period 1 does not enter into any statistical analysis, as it only serves to provide labeling for the cells that allegedly remain and return and are retained in solid tissues. However, Period 1 will permit definition of CLL cell birth rate and disappearance rate (death and permanent return to solid tissue from blood).

An important part of the statistical analysis in Period 2 is characterization of the pattern of LC over time. Patterns will be analyzed both visually and using more formal statistical methods in an exploratory manner. First, the pattern will be smoothed using a cubic spline interpolation (SAS Graph, SAS Institute, Cary, NC). This will facilitate the determination of shape and numbers and patterns of peaks by eliminating “noise” in the data. Second, based on the patterns observed after smoothing, the data will be fit to candidate regression models (e.g., parabolas, mixtures of parabolas, piecewise curves, etc.) and the best fitting model will be identified using common statistical methods such as  $R^2$ , Akaike’s information, etc. All curves will be fit on individual subjects, thereby permitting subjects to vary in the pattern of their LC response curves.

For example, one possible pattern would be an inverted-U parabola (Figure 1), where LC initially increases (presumably, as previously labeled CLL cells are simultaneously retrieved from solid tissue sanctuaries) and then declines (as the solid tissue sanctuaries have been depleted). Another example would be a mixture of two inverted-U parabolas (Figure 2), whereby there are two distinct peaks, suggesting that retrieval of cells from solid tissue may take place at two distinct times. Clearly, many other patterns are possible; however, the most likely candidate patterns are those with some form of initial upward slope, followed by a global peak, followed by a downward slope.

Interim analyses and stopping rules: In order to monitor study progress and success, interim analyses will be done after the first 5 and the first 10 patients have been labeled and treated for 3 months. The study will be placed on hold if the interim analyses determine that in less than 3 out of 5 patients or in less than 6 out of 10 patients, sufficient kinetic biomarker measurements can be obtained to accomplish the study

objectives (for technical and other reasons, such as patient compliance). In this case, the study would need to be modified and can only be re-opened after a protocol revision that addresses such potential technical and/or logistical issues, which needs to be agreed upon among the Principal Investigators and the sponsor. At that time, the investigators together with the sponsor will determine whether the data indicate that the objectives of the study can be met, or whether substantial changes to the protocol or data analyses would become necessary. This interim analysis will, however, not place the patient accrual on hold, unless the interim analyses would come to the conclusion that the study needs to be modified. In addition, at any time during the trial, if we see more than 30% of patients experiencing grade 3-4 non-hematological toxicities, we will stop the trial.

In general, no formal statistical inference is planned (i.e., hypothesis tests or confidence intervals). The analysis is exploratory with the primary objective of discovering patterns of observed labeling that might provide further insights into the kinetics and biology of CLL.

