### **8.9 Sample Collections for H-DNA-labeled Leukemic Cells during PCI-32765 Treatment Phase**

After beginning PCI-32765 therapy, subjects will be seen for follow-up visits including blood draws (60ml) at day 1 (+/- 3 days), day 3 (+/- 1 day), week 2 (+/- 3 days), and every 2 weeks (+/- 3 days) thereafter for a period at least equal in duration to that of the initial H2O washout phase of 6 to 12 weeks. At these visits, clinical and laboratory assessment, which will include blood sampling (60ml) for H2O kinetic measurements, will be made. Subjects will continue to return or be seen by a local physician or clinical laboratory each month (+/- 3 days) for an additional 3 months for blood drawing (60ml). Data obtained from these blood samples will permit a determination of the slope and rate of the appearance of previously labeled CLL cells in the blood, and the slope and rate of the disappearance of labeled cells from the blood. If re-circulation to solid tissues is inhibited by PCI-32765 therapy, the disappearance rate will represent primarily the death rate of leukemic cells *in vivo*. Because during the treatment period, H2O will not be available to label newly-born cells, any cells containing H-labeled DNA will represent cells labeled during the initial period of H2O consumption and retained *in situ*. The kinetic measurements of the entire CLL clone will be compared with those of intracлонаl fractions from the same samples, defined by the reciprocal differences in CXCR4/CD5 surface membrane densities; this approach is described in the published study by Calissano et al. (Mol Med 2011;17: 1374-1382, 2011). In addition, these fractions will be analyzed for:

1. Phenotype and numerical changes of B and T cells and myeloid cells within these fractions, pre- and post-ibrutinib therapy
2. Gene expression profiles of cells within these fractions, pre- and post-ibrutinib therapy
3. DNA methylation profiles of cells within these fractions, pre- and post-ibrutinib therapy.

4. Response to BCR and other signals of cells within these fractions, pre- and post-ibrutinib therapy, using western blots on phosphoproteins/ibrutinib occupancy
5. Differences in engraftment and growth capacities of CLL B and T cells in NSG mice, unseparated or within these fractions, pre- and post-ibrutinib therapy

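### Section 13.0 assumes an on-treatment peak and takes its time from the same noisy series, so a subject with a flat labelled-cell level will usually appear to rise and fall

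*Combined protocol and SAP*

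**What the plan says.** Section 13.0 splits the PCI-32765 period at T: "Assuming that the observed percentage of labeled cells (LC) reaches a peak at some point in time". Period 2a runs up to and including T, and Period 2b is everything later. The section does not say whether T is read from the raw values, the spline or a fitted curve.

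The analysis steps are:

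- Smoothing: "First, the pattern will be smoothed using a cubic spline interpolation", meant to take out noise so that peaks can be seen and counted.
- Fitting: "All curves will be fit on individual subjects, thereby permitting subjects to vary in the pattern of their LC response curves".
- Choice of curve: "the best fitting model will be identified using common statistical methods such as" R² and Akaike's criterion. The named examples are single and mixed parabolas and piecewise curves. The list is open and the section accepts that other shapes may occur.
- Expectation: "the most likely candidate patterns are those with some form of initial upward slope, followed by a global peak, followed by a downward slope". An early rise is read as labelled cells coming out of solid tissue.

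One stated aim is "3) to estimate rates of cell death". Section 8.9 adds that, if the drug blocks return to tissue, "the disappearance rate will represent primarily the death rate of leukemic cells". No tests or confidence intervals are planned, and the analysis is called exploratory. The only provision for a flat response, in Section 14.0, concerns Period 1.

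**The concern.** T is chosen from the same values that are then described on either side of it. Period 2a contains the highest value by construction, so its slope is pushed upward even when nothing is happening. That slope bears on the trial's central question in Section 2.1: how much of the drug's effect is movement of cells out of tissue. With no rule for a subject without a peak, and no test or interval, nothing in the plan would flag an artefact.

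The slope after T is the natural estimate of the death rate, although the plan never says so. Whether it is biased, and in which direction, depends on a choice that the plan leaves open.

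**Working it through.** **Inputs.** The plan gives no figure on this point to reproduce. Draw days follow Sections 8.2 and 8.9 and the Schedule of Events:

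- 12 weeks of draws plus three monthly draws: days 1, 3, 14, 28, 42, 56, 70, 84, 112, 140, 168 (11 draws).
- 6 weeks plus three monthly draws: days 1, 3, 14, 28, 42, 70, 98, 126 (8 draws).
- Schedule of Events, last kinetic draw at week 12: days 1, 3, 14, 28, 42, 56, 70, 84 (8 draws).

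Assumed, because the documents do not give them: an assay coefficient of variation (CV) of 5% or 10%, independent errors unless stated, and true losses of 0, 0.1 and 0.3%/day. The birth rates in Section 2.4 (0.1 to 1.7%/day) serve only as a scale. Loss is minus the slope of log LC. Results come from simulated series, with T taken as the time of the highest observed value.

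**Step 1: where the maximum falls when the truth is flat.** With independent errors each of n draws is equally likely to be the highest, so P(inner draw) = (n − 2)/n. This is 6/8 = 75% with 8 draws and 9/11 = 82% with 11, whatever the CV. Simulation agrees.

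**Step 2: the pre-peak slope when the truth is flat.** Fitted on t ≤ T, where T is later than the first draw, it is positive in 94–98% of series. At 10% CV its mean is +1.2 to +1.5%/day. The median is only 0.2–0.3, because the early draws are close together and give a few very steep slopes.

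**Step 3: the safeguards.** A cubic spline interpolant passes through every observation. Its residual at the data points is 0, so no noise is removed. For model choice I compared a constant, a line, a parabola and a joined two-piece line on flat data:

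| Criterion | False rise-fall chosen |
|---|---|
| R² | about 42% (never chooses the constant) |
| AIC | about 12–16% |
| AICc | about 1% or less |

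**Step 4: the post-peak loss rate.** Mean estimates in %/day, 11 draws, at least three points per fit:

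| True loss | CV | t > T, as written | t ≥ T, peak included |
|---|---|---|---|
| 0 | 5% | 0.00 (positive in 50%) | 0.055 (positive in 87%) |
| 0 | 10% | 0.00 (positive in 49%) | 0.108 (positive in 87%) |
| 0.1 | 5% | 0.093 | 0.117 |
| 0.1 | 10% | 0.087 | 0.158 |
| 0.3 | 5% | 0.294 | 0.307 |
| 0.3 | 10% | 0.288 | 0.324 |

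With 8 draws to week 12, the peak-included values for a flat truth rise to 0.13 at 5% CV and 0.26 at 10%. Other routes to a false loss on flat data at 10% CV:

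- T from the spline, then raw points after it: 0.04–0.11.
- Slope of the spline curve after its peak: 0.07–0.19.
- t > T with serial correlation of 0.5 per two weeks: 0.05–0.11.

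**Step 5: the alternative.** A joint change-point fit to all draws, averaged over all series whatever their shape, gave −0.002 to +0.007 for a flat truth, 0.087–0.099 for a true 0.1 and 0.295–0.307 for a true 0.3%/day.

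**Step 6: how strict AICc is.** The penalty is 2p + 2p(p + 1)/(n − p − 1), with p = 2 (constant), 4 (parabola) and 5 (two-piece, counting the change-point and the variance). A curve beats the constant when its R² exceeds 1 − exp(−difference in penalty/n).

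- n = 8: penalties 6.4, 21.33 and 40. R² must exceed 1 − exp(−14.93/8) = 0.845 for the parabola and 1 − exp(−33.6/8) = 0.985 for the two-piece line.
- n = 11: penalties 5.5, 14.67 and 22. The thresholds are 1 − exp(−9.17/11) = 0.565 and 1 − exp(−16.5/11) = 0.777.

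**The case against.** The strongest reply is that Period 2b is defined as times after T, so the value selected for being high is not in it. This stands. A reader might infer that the plan's death rate is biased upward as written. With independent errors it is not: the bias is zero for a flat truth, and a true decline comes out slightly low. A reader might also infer that every subject will show a rise and a fall. That is too strong, because a maximum at the first draw leaves no rise and one at the last draw leaves no fall.

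It is also fair that the plan never equates T with the raw maximum or the death rate with the Period 2b slope. Its candidate list is open, it already names Akaike's criterion, and a piecewise fit to all draws is close to the remedy proposed here. The study is exploratory and no decision rests on this slope.

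These points limit the consequences but do not remove the defect. The split presumes a peak, R² is offered alongside AIC without a preference, and interpolation cannot do what it is meant to do. AIC alone still gives a false rise-fall in about one flat series in seven. An exploratory search for patterns needs some guard against patterns made by noise, and here there is none that works.

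**Conclusion.** The point holds for the assumed peak, the pre-peak slope and the choice of curve. With T read as the observed maximum, 75–82% of truly flat subjects would show an inner peak, and about 95% of the pre-peak slopes that can be fitted would be positive. The first figure needs only independent errors of equal spread; it does not depend on the CV.

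For the post-peak loss rate the finding is narrower. The written window gives 0.00%/day for a flat truth and 0.08–0.09 for a true 0.1%/day. Upward bias arises if the peak value enters the fit (about 0.05–0.13%/day at 5% CV and 0.11–0.26 at 10% for a flat truth), for example through a joined piecewise or spline curve, or if errors are serially correlated. The plan does not exclude these routes. The sizes rest on assumed CVs and matter mainly when true loss is slow.

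**What to change.** Change the wording of Section 13.0 as follows:

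1. Estimate T and the rise and fall slopes together from all on-treatment draws, with a change-point or rise-fall model on log LC, instead of splitting at the observed peak.
2. Add flat and monotone models to the named candidates.
3. Drop R² and select by AICc.
4. Use the interpolating spline for display only, or replace it with a smoothing spline.
5. Report a release peak and a post-peak rate only where a rise-fall model is selected, and report the other subjects as having no clear peak.

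The data and draws are unchanged, so the cost is wording and a different fit. The downside is lower sensitivity. As Step 6 shows, AICc is strict with 8 draws, so some true peaks, the small ones above all, will go unconfirmed in single subjects. Rates reported only after selection can also still be somewhat high where a peak is small. A mixed-effects version that shares information on T across subjects is optional and would ease both problems, while still allowing subjects to differ.

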**4.0 Objectives**

The primary objective is to assess the impact of the Bruton's tyrosine kinase (Btk) inhibitor PCI-32765 on leukemia cell trafficking and death using heavy water ( $^2\text{H}_2\text{O}$ ) labeling of newly-born malignant cells in subjects with Chronic Lymphocytic Leukemia (CLL) and Small Lymphocytic Lymphoma (SLL).

The secondary objective is to determine the percent of recently born versus older leukemia cells mobilized into the blood by PCI-32765 treatment.

The tertiary objective is to compare the kinetic biomarker measurements in CLL subjects to other established prognostic tests and response to therapy with PCI-32765.

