## 5.0 Study Design

This is a one center, open label pilot study to evaluate the impact of the Btk inhibitor PCI-32765 on leukemia cell trafficking and death, using heavy water labeling in subjects with Chronic Lymphocytic Leukemia (CLL) and Small Lymphocytic Lymphoma (SLL). PCI-32765 will be supplied by Pharmacyclics as capsules containing 140mg of PCI-32765. Subject grade  $^2\text{H}_2\text{O}$  will be purchased from KineMed, Inc, and KineMed will analyze *in vivo* incorporation of  $^2\text{H}$  into deoxyadenosine of B lymphocytes by GC/MS. A total of 30 subjects are to be enrolled at MD Anderson Cancer Center.

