## 14.0 Sample Size Considerations

This is primarily a (structured) exploratory study to discover patterns of cell kinetics in CLL. There are no data from previous experiments that would permit specification of a formal alternative hypothesis for which a power or precision calculation could be made. The proposed sample size is 30 subjects of which it is expected that 18 (approximately 60%) will be evaluable. An evaluable patient for the purpose of this protocol is primarily defined as a patient who has been able to adhere to all protocol-required procedures and blood draws during the heavy water labeling period, the resting period, and during treatment with PCI-32765. In addition, to be considered an evaluable patients, sufficient material with detectable levels of heavy water-labeled CLL cells must be recovered from the blood specimen by our colleagues at the Feinstein Institute and at KineMed, Inc. Specifically, it is expected that about 20% of subjects will exhibit a delayed release of labeled cells into the circulation in Period 1, which will manifest itself as an initially “flat” response; this number is based on available information from previous studies of this type. These subjects will be excluded from both the Period 1 and 2 analyses, but may be analyzed separately. In addition, it is anticipated that 20% of subjects will not be able to delay treatment for the desired 12-16 weeks post-labeling. These subjects will also be excluded from both the Period 1 and 2 analyses, but their data may be analyzed and used separately. The proposed sample size is consistent with other studies in CLL using similar methodologies. If necessary, the overall accrual will be increased in order to yield at least 20 evaluable subjects.

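### No analysis compares Period 2 with the same subject's untreated Period 1b, the only off-drug reference for a primary objective about the drug's impact, and Sections 13.0 and 14.0 disagree on whether Period 1 is analysed

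*Combined protocol and SAP*

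**What the plan says.** Section 4.0: "The primary objective is to assess the impact of the Bruton's tyrosine kinase (Btk) inhibitor PCI-32765 on leukemia cell trafficking and death". Section 5.0 describes "This is a one center, open label pilot study to evaluate the impact of the Btk inhibitor PCI-32765" and no comparison group. Every subject has four weeks of labelling, a rest without drug, and then PCI-32765.

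Section 8.2 schedules blood draws every two weeks during the rest. Section 8.9 continues draws on drug "for a period at least equal in duration to that of the initial" washout phase. It also describes any labelled cell seen on treatment as one that was labelled earlier and stayed in place.

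Section 13.0 gives three statements about Period 1:
- heavy water is stopped in Period 1b "so that a CLL cell disappearance rate can be tracked over time";
- "Strictly speaking, Period 1 does not enter into any statistical analysis, as it only serves to provide labeling for the cells";
- immediately afterwards, "However, Period 1 will permit definition of CLL cell birth rate and disappearance rate".

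Smoothing, candidate curves and the peak time T are all described for Period 2. An initial rise is read, tentatively, as retrieval from tissue, and the later fall as depletion.

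Section 14.0 expects that "about 20% of subjects will exhibit a delayed release of labeled cells into the circulation in Period 1". It excludes these subjects from the analyses of both periods, which implies that a Period 1 analysis exists.

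**The concern.** Impact means the difference between what happened on drug and what would have happened without it. With no control group, each subject's own Period 1b is the only untreated reference. It is sampled on the same two-weekly rhythm as Period 2, and Period 2 sampling lasts at least as long, so the data suit a before/after comparison. The plan does not make one.

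This matters because the labelled percentage in blood (LC) need not be steady when drug starts. Cells labelled in tissue can still be entering the blood, or LC can already be falling as unlabelled cells are born. A Period 2 curve alone cannot separate either trend from a drug effect. Section 2.1 says the balance between redistribution and effects on proliferation could bear on how the drug is developed, so the distinction has consequences even in an exploratory study.

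**Working it through.** **1. The plan's own count.** Section 14.0 expects 20% of 30 subjects to show delayed release and 20% to be unable to delay treatment: 30 − 6 − 6 = 18 evaluable, as stated. The plan gives no power or precision figure to reproduce.

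**2. What is and is not analysed.** Section 13.0 first rules Period 1 out, then has rates defined from it. Section 14.0 refers to analyses of both periods. Rates will thus exist, but no section compares them, or the Period 1b course, with Period 2.

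**3. Can LC move on its own after drug start?** Illustration with no drug effect.

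Inputs from the documents:
- labelling for 28 days (Section 8.1);
- rest of 6–12 weeks (Section 8.2), so drug starts between day 28 + 42 = 70 and day 28 + 84 = 112;
- birth rate b between 0.1% and 1.7% per day, with a cut at 0.35% (Section 2.4). I use 0.35% and 1.0%.

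Assumptions:
- blood–tissue exchange k of 0.5%, 1%, 2% or 5% per day (the documents give no figure);
- birth in tissue only, label fully on for days 0–28 and off afterwards, no transit lag.

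Tissue: dT/dt = b(L − T), with L = 1 to day 28 and 0 after. Blood: dB/dt = k(T − B).

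Up to day 28, B(t) = 1 − e^(−kt) − [k/(k−b)]·(e^(−bt) − e^(−kt)). With s = t − 28, later values are B(28)·e^(−ks) + T(28)·[k/(k−b)]·(e^(−bs) − e^(−ks)).

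Worked case, b = 0.0035 and k = 0.02:
- T(28) = 1 − e^(−0.098) = 9.34%; B(28) = 2.22%.
- B(70) = 2.22% × 0.4317 + 9.34% × 1.2121 × (0.8633 − 0.4317) = 5.84%.
- B(112) = 6.74%. Change from day 70 to 112: 6.74/5.84 − 1 = +15%.

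Six-week change in LC with no drug effect:

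| k per day | b = 0.35%: untreated peak | from day 70 | from day 112 | b = 1.0%: from day 70 | from day 112 |
|---|---|---|---|---|---|
| 0.5% | day 252 | +47% | +20% | +29% | +5% |
| 1% | day 176 | +34% | +10% | +16% | −6% |
| 2% | day 120 | +15% | −3% | −4% | −21% |
| 5% | day 73 | −7% | −13% | −27% | −33% |

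A longer rest shrinks the spurious rise but leaves a drug-free decline. From day 140 (16 weeks, the upper end in Section 14.0), the b = 0.35% changes are +12%, +3%, −7% and −13%.

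**4. Which comparisons survive the drift?**
- *Early change.* At b = 0.35%, drug-free change from day 70 to day 73 is at most about +4%. A jump between drug days 1 and 3 would stand out; slow mobilisation would not.
- *Straight-line projection.* A line through days 42, 56 and 70 overshoots. The true drug-free day-112 value lies 12–26% below it at b = 0.35% and 19–32% below it at b = 1.0%. A linear carry-forward would report negative mobilisation where there is none.
- *Disappearance rates.* Off drug, Section 8.2 defines the rate as death together with movement back to tissue. On drug, Section 8.9 reads it as mainly death, if recirculation is blocked. Their difference is not drug-induced death.

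**The case against.** Three stronger readings are tempting, and the documents do not support them.

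- *Period 1 is discarded.* It is not. The sentence after the exclusion has birth and disappearance rates defined, Section 8.2 schedules draws for that purpose, and Section 14.0 refers to a Period 1 analysis. What is missing is the comparison.
- *Natural release is credited to the drug.* No rule does this. Section 13.0 offers the rise-and-fall as one possible pattern, explains it only presumptively, classifies no subject and plans no formal inference.
- *The primary objective cannot be answered.* The early draws on drug give a short within-subject contrast that drift barely touches.

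The plan also foresees late release and excludes those with an initially flat Period 1 response, which removes the plainest cases. This safeguard is partial: flat has no numerical definition, and moderate late release or ongoing decline stays in.

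The day-70 figures are the less favourable end of the 6–12 week range. If Section 14.0's longer rest governs, such a subject would not be in the main analysis at all. The day-112 figures are therefore shown beside them.

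The figures in Section 13.0 were not available in the text reviewed. The text cites them as example Period 2 patterns; a drawing of both periods would not in any case specify a comparison.

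**Conclusion.** The point stands as a gap and an inconsistency. Sections 13.0 and 14.0 disagree on whether Period 1 is analysed, and no section compares Period 2 with the subject's own untreated course, although the objective requires it and the draws are planned. A slow rise or fall on drug may therefore include untreated change.

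At a birth rate of 0.35%/day that change could be +47% to −7% over six weeks from a day-70 start, or +20% to −13% from day 112. These sizes rest on an assumed exchange rate and a two-compartment model. They show that a rise or fall can occur without drug, not that it will. Whether a given subject was still rising or already falling can be seen only in that subject's Period 1b data.

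**What to change.** Delete the sentence that keeps Period 1 out of the analysis and state a descriptive within-subject comparison. No tests are needed.

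1. Plot Periods 1 and 2 on one time axis for each subject.
2. Fit each subject's Period 1 data with a saturating label-and-dilution curve, not a straight line, and report the Period 2 departure from its projection. State the model assumption and give a sensitivity range. Report the day 1 to day 3 change alongside, using actual draw dates, because the two visit windows (±3 days and ±1 day) overlap.
3. Report Period 1b and Period 2b disappearance rates side by side with their difference, as signed slopes, since some subjects may still be rising. Label them net loss from blood: death plus redistribution off drug, and mainly death on drug only if recirculation is inhibited. Do not label the difference drug-induced death.
4. Reword Section 8.9 so that labelled cells already circulating at first dose are not described as having remained in tissue.
5. Give a numerical definition of a flat Period 1 response.
6. Reconcile the rest lengths: 6–12 weeks in Section 8.2, under 6 weeks with approval in the same section, and 12–16 weeks in Section 14.0. They govern how large the drift is.

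Cost: revised wording and modest extra analysis, with no new draws. The contrast is noisier than Period 2 alone and depends on the projection model. As a guide, with 18 evaluable subjects the mean of a within-subject difference has a 95% interval half-width of 2.11/√18 = 0.50 SD; the documents do not give the SD.

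### The on-treatment labelled-cell curves are judged partly by eye in an open-label study, with no masking of that reading to the response and prognostic data the kinetics are later compared with

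*Combined protocol and SAP*

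**What the plan says.** Section 5.0 opens: "This is a one center, open label pilot study". Section 13.0 describes the analysis of the percentage of labelled cells during treatment (Period 2) as follows.

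- General approach: "Patterns will be analyzed both visually and using more formal statistical methods in an exploratory manner".
- The curve is smoothed with a cubic spline. Of this step the plan says: "This will facilitate the determination of shape and numbers and patterns of peaks".
- Then "based on the patterns observed after smoothing, the data will be fit to candidate regression models". The examples are parabolas, mixtures of parabolas and piecewise curves, and the list is left open. Fitting is done subject by subject.
- Finally, "the best fitting model will be identified using common statistical methods such as" R-squared and Akaike's information.
- Period 2 is cut at the peak time T, with times up to T forming Period 2a and later times Period 2b.

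Section 14.0 expects about 20% of subjects to show an initially flat response in Period 1 and excludes them from the analyses of both periods. It gives no threshold for flat. The tertiary objective in Section 4.0 is to "compare the kinetic biomarker measurements in CLL subjects to other established prognostic tests and response to therapy with PCI-32765".

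**The concern.** The label itself is measured by GC/MS and leaves little to opinion. The step from measurements to a described curve does involve judgement: what counts as a peak, which peak defines T, which models are worth fitting, and whether a subject is flat. The plan does not say who makes these judgements, what else that person may see, or when the result is recorded.

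This matters because the kinetic results are later set against response and prognostic markers. A reader who knows that a subject responded well, or carries adverse markers, may settle an unclear curve in the direction expected. Part of any association would then come from the reading. With about 18 evaluable subjects and no planned tests or intervals, the described patterns and rates are the study's result, and a later reader could not separate the two sources.

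**Working it through.** **1. What can be known when a curve is read.** IGHV, CD38, ZAP-70 and FISH come from the screening marrow (Section 7.0). Labelling takes 4 weeks and the rest period 6 to 12 weeks (Sections 8.1 and 8.2), so the markers are sampled at least 4 + 6 = 10 weeks before treatment starts, and 4 + 12 = 16 weeks with the longest rest.

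Section 8.9 calls for treatment-period draws on day 1, day 3, week 2 and every 2 weeks for at least as long as the washout, then monthly for 3 months. Taking a month as 28 days (my assumption):

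- 6-week washout: days 1, 3, 14, 28, 42, 70, 98, 126, which is 8 draws.
- 12-week washout: days 1, 3, 14, 28, 42, 56, 70, 84, 112, 140, 168, which is 11 draws.

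The first response assessment is due after cycle 3 (Section 11.0), at 3 × 28 = 84 days. A complete curve exists only at day 126 to 168. Response after cycle 3 is therefore due before any complete curve can be read.

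**2. How the reading reaches a number.** Section 13.0 does not say whether T is the largest observed value, the top of the spline or the top of the fitted model. It allows for curves with two peaks without saying which one sets T. As an illustration, these are the draws in Period 2a and 2b for three possible readings of T:

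| T read as | 8 draws: 2a / 2b | 11 draws: 2a / 2b |
|---|---|---|
| day 28 | 4 / 4 | 4 / 7 |
| day 42 | 5 / 3 | 5 / 6 |
| day 70 | 6 / 2 | 7 / 4 |

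Moving T by one visit, from day 28 to day 42, takes one draw out of the disappearance slope and puts it into the appearance slope. Choosing a second peak at day 70 over a first at day 28 leaves 2 of 4 post-peak draws on the short schedule and 4 of 7 on the long one.

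**3. The flat call.** Section 14.0's figure reproduces: 30 × (1 − 0.20 − 0.20) = 18 evaluable. The flat group accounts for 30 × 0.20 = 6 subjects. They leave both period analyses on a judgement of shape that has no stated rule or time of decision. Markers are known by then, and response may be if the call is made at analysis.

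**4. What the comparison uses.** The tertiary objective concerns kinetic measurements. Sections 8.2, 8.9 and 13.0 describe these as birth rate, disappearance rate, and slopes of appearance and disappearance. The Period 2 slopes depend on T. The birth rate is defined from Period 1, so the Period 2 reading does not touch it; only the flat exclusion does.

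**5. Masking.** No section keeps response or marker data from the person reading the curves, and none requires the reading to be recorded before those data are linked.

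**The case against.** Several things count against the point.

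- **Model choice is not visual.** A reader might infer that the model itself is picked by eye. Section 13.0 does not support that, because the final choice rests on R-squared, Akaike's information and similar. What stands is that the candidates are proposed after viewing the curve, and more than one criterion is named.
- **The comparison is mostly numeric.** A reader might infer that pattern class or peak count is what gets compared with response. No section says so. The earlier CLL work in Section 2.4 related a numeric birth rate, cut at 0.35% per day, to disease activity. This narrows the route to T, the 2a/2b split and the flat exclusion. If T were simply the largest observed value, only the flat call would remain, but the plan does not say that.
- **The reader is not identified.** Outside groups recover the cells and measure the label, and whoever reads the curves may hold no clinical data. That is possible but not stated.
- **Some samples are de-identified.** A reader might infer that nothing in the study is coded. Section 10.0 removes identifiers from samples sent out for optional research testing. That is a confidentiality measure and is not stated for the kinetic reading, so the supportable statement is only that no masking of the kinetic reading is described.
- **Interim looks.** A reader might infer that the looks after 5 and 10 patients expose kinetic results to those assessing response. Section 13.0 frames them as a count of subjects with sufficient measurements, so they do not support the point.
- **Low stakes.** No formal inference is planned, the study is exploratory, and the comparison is tertiary. This limits the severity but does not remove the route.

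**Conclusion.** The point holds as a low-severity improvement. A partly visual, unmasked reading can shape the Period 2 slopes and the analysed set, which then enter a comparison with variables the reader may know.

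Its size cannot be given. A reader might want a number of percentage points, but the documents state neither the assay variation nor how many curves would be ambiguous. Even in the simplest case, with no true link, a share q of ambiguous curves, and a probability b that each is read in line with response, the expected false difference in pattern frequency is q × (2b − 1). That runs from 0 (b = 0.5) to q (b = 1) and only returns what was assumed. It also concerns pattern frequency, not the slopes.

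The conclusion assumes that the reader has access to clinical data, which the plan neither states nor prevents, and that T depends on how the curve is read. It does not reach the GC/MS values, and it reaches the birth rate only through the flat exclusion.

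**What to change.** Add to Section 13.0, in substance:

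> Curves will be plotted under a study code, without response, prognostic or other clinical data. For each subject the flat call, pattern, number of peaks, T and selected model will be recorded and locked before linkage to those data. The rule for a peak and one model-selection criterion will be fixed before any curve is read.

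The peak rule should also say which peak sets T when there are two, and the flat call needs a stated threshold.

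One criterion is needed because R-squared never falls when terms are added to a nested model, while Akaike's information penalises them, so the two can disagree. AICc is a reasonable choice for short series, but it must be computable. Its added term is 2k(k + 1)/(n − k − 1). A single parabola has k = 4 (three coefficients and a residual variance), giving 40/3 = 13.3 at n = 8 and 40/6 = 6.7 at n = 11. Two separate parabolas, assuming six coefficients and a variance, have k = 7. The term is then 112/3 = 37.3 at n = 11, and undefined at n = 8 because the denominator is 0. The rule should say how such models are handled on the short schedule.

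The same reader and analyst can do all this. It needs no extra sample, visit or subject, and does not change the sample size. The cost is a code list, a lock step and a short wait before kinetic and clinical data can be viewed together.
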